Nutrients and enteral hormones (e.g., CCK, GLP-1) released in response to nutrients also stimulate small intestinal mechano and chemoreceptors or tastant receptors, which are located on or activate vagal afferents. Few studies have explored the contribution of duodenal sensitivity to symptoms in functional dyspepsia. Duodenal acidification induces proximal gastric relaxation, increases sensitivity to gastric distension, and inhibits gastric accommodation to a meal⁷. Duodenal lipid infusion increased the sensitivity to gastric distension in functional dyspepsia⁸⁻¹¹. This sensitizing effect was blocked by a lipase inhibitor or a CCK-A receptor antagonist^{12,13}. We recently observed increased sensitivity to duodenal nutrient (carbohydrate and lipid perfusion) in approximately 50% of patients with functional dyspepsia during lipid and separately carbohydrate infusion, without gastric distention (unpublished observations). Moreover, increased sensitivity was associated with higher plasma concentrations of CCK during lipid infusion and more severe dyspeptic symptoms during daily life. However, the contribution of intestinal chemosensitivity to symptoms in DM is unknown. We recently observed that patients with functional dyspepsia reported more severe symptoms during enteral lipid and carbohydrate infusion. Second, this increased sensitivity was associated with higher plasma concentrations of enteral hormones (e.g., GLP-1 during lipid and carbohydrate infusion), more severe dyspeptic symptoms, and a greater impact on quality of life.

Vagal dysfunction has been implicated as a mechanism for GI sensorimotor dysfunctions in DM¹⁴. The plasma pancreatic polypeptide (PP) response to sham feeding evaluates GI vagal function¹⁵. In clinical practice, assessment of cardiovascular vagal functions is used as a surrogate measure of GI vagal dysfunction. Only 1 study evaluated the relationship between cardiovascular and GI vagal dysfunction (i.e., gastric acid secretion, PP response to sham feeding) and observed a modest correlation¹⁵. The utility of the sham feeding response and cardiovascular measures to predict upper GI sensorimotor dysfunctions has not been evaluated.

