3.3 Details of Study Assessments

In patients with DM, fingerstick bedside reflectance meter blood glucose concentrations will be assessed during enteral infusion and gastric emptying studies at time 0, every 30 minutes for 2h, then at 120 and 180 minutes. For patients with type 1 and type 2 DM who are treated with insulin, insulin will be given according to the patient's sliding scale. For type 2 DM patients who are not on insulin, no insulin will be given.

i) Screening items include questionnaires (for overall functional GI symptoms [Rome III criteria], severity of dyspepsia [Nepean severity index], gastroparesis cardinal symptom index [GCSI], anxiety and depression [HAD], and autonomic symptoms), blood tests (CBC, glycosylated hemoglobin, fasting glucose, sodium, potassium, bicarbonate, calcium, chloride, phosphorous, AST, total bilirubin, alkaline phosphatase, creatinine, high sensitive C-reactive protein, tissue transglutaminase antibodies, and lipase), and EKG (to be reviewed by study physician). Some patients with diabetes mellitus have low serum lipase. Patients with serum lipase < lower limit of normal (i.e., < 10 IU/ml) will not be eligible to participate in the study.

Study procedures will be conducted over 3 days. Items (ii), (iii), (iv), and (v) below will be performed on the same day preferably before other study procedures. A tentative schedule is as follows: (ii) between 8 and 8.45 am, (iii) between 8.45 am and 11 am, (iv) can start while (iii) is in progress and (v) between 12.30 pm and 3 pm.

ii) Plasma pancreatic polypeptide (PP) response to sham feeding. Pancreatic polypeptide (PP) is secreted by the pancreas in response to hypoglycemia, ingestion of food or sham feeding secondary to vagal nerve stimulation. Vagal nerve injury blocks secretion. This assessment will be performed in the Charlton 7 CRU. Subjects will be fasting with NPO for 8 hours prior to this test. They must abstain from coffee or for 12 hours and stop all cholinergic agents for 48 hours before the test. During the sham feeding test, food is chewed and spit out (not swallowed) . After placement of an IV in the hand or forearm vein for blood draws, this hand will be placed in a hotbox heated to 55°C. Blood will be drawn in a lavender-top (EDTA) tube(s) at -5, 0, 5, 10, 15, 20, 25, and 30 minutes for PP. Spin down, keep specimen cold, and send 1.0 mL (0.5 mL minimum) of EDTA plasma frozen in plastic vial.

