v) Hormonal responses and symptoms during duodenal infusions. A small bore nasogastric tube will be inserted through the nostril into the stomach over a guidewire and advanced under fluoroscopic guidance until the infusion ports are in the 2nd part of the duodenum.

Thereafter, subjects in each group (ie, functional dyspepsia and DM) will be randomized to lipid infusion {66.7 mL Microlipid (0.5 gm/mL diluted in water to 222 ml)} together with placebo or exendin 9-39 in the ratio of 1:1. Lipids will be delivered into the duodenum at an infusion rate which matches the rate at which glucose enters the systemic circulation after oral glucose. After placement of an IV in the hand or forearm vein for blood draws, this hand will be placed in a hotbox heated to 55°C. We have considerable preliminary data for symptoms and hormonal responses with this paradigm. Plasma glucose, insulin, C-peptide, GLP-1, CCK, ghrelin, and PYY will be collected at 5 minute intervals for 30 minutes, 10 minute intervals from 30 – 60 minutes, and at 15 minute intervals from 60 – 180 minutes (18 times including 0 minutes).

vi) GLP-1 antagonist exendin 9-39 will be sourced from C.S. Bio, reconstituted in the Mayo Pharmacy by an established process used in previous studies, and undergo endotoxin testing, sterility testing and bacterial testing, and held in quarantine before it will be used in humans. Research compounded sterile preparations (CSP) are prepared and assessed for end preparation testing according to USP <797> in the hospital pharmacy services production lab. Each batch is tested for sterility according to USP <71> utilizing membrane filtration. The sterility testing is validated by a formulation Bacteriostasis Fungistasis test. The amount of each batch tested is determined by USP <71>. Each batch is tested for endotoxin according to USP <85>. High risk CSP are quarantined for 14 days and when all end preparation testing is completed.

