3.5 Data Analysis

Chemosensitivity will be measured using a 100mmVAS anchored at each end (left end:No symptoms, right end: Severe symptoms). The distribution of this measure will be checked for its approximation to a gaussian distribution. An analysis to provide preliminary data for a new grant submission will be examined after approximately 15 subjects (5 DM, 10 controls) have completed the studies, but there is no intention of stopping the study based on the preliminary results. We anticipate conducting this analysis in July 2014 or thereafter.

Question	Summary Parameter	Statistical analysis
Sensation (symptoms) during enteral infusion (Aim 1)	VAS score	i) compare VAS scores in response to lipid infusion + exendin vs. lipid infusion + placebo separately for each group using a 2-sample t-test or Wilcoxon rank sum test ii) compare the delta VAS scores (exendin – placebo) to assess the association with subject status (FD,DM, and controls) using an ANOVA model (adjusting for covariates, eg, type of DM) or Kruskal-Wallis test.
Relationship between intestinal chemosensitivity and severity of ongoing upper GI symptoms	Mean symptom score and QoL defined by the Nepean dyspepsia index and GCSI diary	Multiple linear regression with the dependent variable = mean symptom score, and separately the QoL score (possibly after rank transformation). Potential predictor variables = VAS score during enteral lipid + placebo infusion, gastric emptying, age, gender, BMI
Relationship between sensation and plasma hormones during lipid infusion (Aim 2)	Using the VAS score from the enteral infusions and for hormones, the AUC values	Spearman correlations between the VAS score and the AUC values for the various hormones, overall and separately by group (FD,DM, controls)
Small intestinal tight junction proteins,	Protein expression, lactulose:mannitol	Assess the associations between permeability and protein expression, vs. the VAS score, based on Spearman

permeability, intestinal chemosensitivity	ratio, VAS score	correlations.
---	------------------	---------------

The sample size estimate is based on our previous study which evaluated intestinal chemosensitivity in functional dyspepsia in which the proportions with severe symptoms were assessed. [In the current proposal, symptoms during lipid infusion will be evaluated on a continuous VAS scale, likely providing the ability to detect smaller effect sizes]. The effect of lipid plus

Group	Proportions (%) with severe symptoms			

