	exendin+lipid vs. placebo+lipid	Controls vs. FD (exendin+lipid)	Controls vs. DM (exendin+lipid)	FD vs. DM (exendin+lipid)
Controls(n=12 vs n=12)	10% vs. 68%	10% vs. 60%	10% vs. 60%	30% vs. 73%
functional dyspepsia (n=20 vs. 20)	10% vs. 50%			
DM (n=20 vs. 20)	10% vs. 50%			

placebo vs. lipid plus exendin in response to enteral infusion can be based on a comparison of the proportions with severe symptoms using a two sample t-test. The association of group status with response to lipid plus exendin can also be assessed using a two-sample t-test for proportions. There is ~80% power (alpha =0.05, 2-sided) to detect the specified differences listed in the table below.

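### The randomised exendin-versus-placebo comparison is valid but unadjusted; in the patient groups, adjusting for the screening Nepean score alone would probably gain precision

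*Combined protocol and SAP*

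**What the plan says.** **Planned test.** Section 3.5, table row 1(i), compares VAS scores under lipid plus exendin and lipid plus placebo "separately for each group using a 2-sample t-test or Wilcoxon rank sum test". No covariate is named. This is the only randomised contrast in the study, and it addresses Aim 2B.

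**Where adjustment does appear.** Row 1(ii) compares the exendin-minus-placebo difference across FD, DM and controls "using an ANOVA model (adjusting for covariates, eg, type of DM) or Kruskal-Wallis test". Row 2 places the daily symptom score on the outcome side and the VAS among the predictors. Neither row uses symptom severity to sharpen the randomised contrast.

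**Available baseline.** The screening items in section 3.3(i) include "severity of dyspepsia [Nepean severity index], gastroparesis cardinal symptom index [GCSI". Randomisation comes later, on the infusion day once the tube is in place, "together with placebo or exendin 9-39 in the ratio of 1:1" within each group (section 3.3(v)). No VAS before the infusion is described.

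**Link between baseline and outcome.** Section 1 reports from unpublished data in FD that "increased sensitivity was associated with higher plasma concentrations of CCK during lipid infusion and more severe dyspeptic symptoms during daily life"; section 2 repeats the link with daily symptoms. No coefficient is given. For DM, section 1 describes the contribution of chemosensitivity to symptoms as unknown, and Aim 1B makes it a hypothesis.

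**Size.** The section 3.5 power table has 20 versus 20 in FD, 20 versus 20 in DM and 12 versus 12 in controls.

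**The concern.** With 20 patients per arm, differences between people in how strongly they react to duodenal lipid make up most of the error in the exendin comparison. If patients with worse daily symptoms also react more strongly, as the protocol reports for FD, part of that error can be predicted from a score already in hand at randomisation. A test that ignores the score leaves that part in the standard error.

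What is at stake is the width of the interval for the exendin effect in FD and DM, and the chance of detecting a moderate effect. The choice also has to be made in advance: an adjustment added once the arms have been seen to differ in severity would carry little weight.

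**Working it through.** **1. The plan's own figure.** Section 3.5 states: "There is ~80% power (alpha =0.05, 2-sided) to detect the specified differences listed in the table below". For FD and DM the difference is 10% versus 50% with severe symptoms, 20 per arm. With the pooled-variance formula, power = Φ[(|p1 − p2| − 1.96·SE0)/SE1]:

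- SE0 = √(2 × 0.30 × 0.70/20) = 0.145
- SE1 = √[(0.10 × 0.90 + 0.50 × 0.50)/20] = 0.130
- power = Φ[(0.40 − 0.284)/0.130] = 81.3%

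This reproduces the stated value. However, it concerns a dichotomised outcome. The documents give no SD or target difference for the VAS, so the calculation below is in SD units.

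**2. Inputs.**

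- From section 3.5: n = 20 per arm (FD, DM) or 12 per arm (controls); two-sided alpha 0.05.
- Assumed: a true difference d = 0.8 SD; a within-group correlation r between screening Nepean and infusion VAS of 0 to 0.5; the same slope in both arms.

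**3. Formulas.** For k baseline covariates, of which only the Nepean score predicts VAS:

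- variance ratio v = (1 − r²) × [1 + k/(2n − 3 − k)]; the second factor is the average cost of chance covariate imbalance
- error degrees of freedom = 2n − 2 − k
- power from the noncentral t with noncentrality (d/√v)/√(2/n)
- effective n per arm = n/v

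Worked case (n = 20, k = 1, r = 0.5): v = 0.75 × (1 + 1/36) = 0.771; effective n = 20/0.771 = 25.9; noncentrality = (0.8/0.878)/0.316 = 2.88 on 37 df; power 80.1%.

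**4. Results at d = 0.8, 20 per arm.** The plain t-test has 69.3%.

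| r | v, Nepean only | Effective n per arm | Power, Nepean only | Power, Nepean + age + gender* |
|---|---|---|---|---|
| 0 | 1.028 | 19.5 | 68.1% | 65.5% |
| 0.3 | 0.935 | 21.4 | 72.2% | 69.6% |
| 0.4 | 0.863 | 23.2 | 75.5% | 73.0% |
| 0.5 | 0.771 | 25.9 | 80.1% | 77.7% |

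*Assuming age and gender do not predict VAS.

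The break-even correlation is about 0.17 with the Nepean score alone and about 0.29 with all three covariates.

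**5. Same calculation at the effect where the t-test has 80% power (0.909 SD, 20 per arm).** Nepean-only power is 78.9% (r = 0), 82.5% (0.3), 85.4% (0.4) and 89.0% (0.5). At r = 0.5 the difference detectable with 80% power falls from 0.91 to 0.80 SD. A simulation of 20,000 runs at r = 0, 0.3 and 0.5 agrees within about half a point.

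**6. Controls, 12 per arm.** Section 3.2 excludes controls with current functional gastrointestinal symptoms, so their Nepean scores should lie near the floor and r near 0. At d = 0.8 the t-test has 46.6%. At r = 0, adjustment lowers this to 44.6% with one covariate and 40.6% with three.

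**7. Chance imbalance.** With simple 1:1 allocation and 20 per arm, a baseline difference above 0.3 SD arises with probability 2[1 − Φ(0.3/√(2/20))] = 2[1 − Φ(0.949)] = 34%. The documents describe no stratification by severity.

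**The case against.** The strongest reply is that a two-sample test after 1:1 randomisation is valid. Its standard error and type I error already allow for chance imbalance, so nothing is wrong with the plan. That stands in full. A reader might infer from the 34% figure that the unadjusted result would be biased; it would not be. Adjustment corrects for imbalance only as far as the score predicts VAS.

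A reader might also infer that the precision is free, or that the Nepean score is an established predictor in every group. The documents support neither. The reported association is for FD, is unpublished and has no coefficient. For DM the relationship is one of the study's own questions. In controls the score should have little spread. Patients are selected for dyspepsia, which may narrow the range of scores and lower r in FD and DM as well. At r below about 0.17, adjustment loses a little power.

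A fuller model with age and gender is tempting, but the documents do not say that either predicts the infusion VAS. Row 2 lists them only as potential predictors of daily symptoms. At r = 0.3 they cancel almost the whole gain (69.6% against 69.3%).

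These objections limit the point to one covariate in the patient groups. They do not remove it: in those groups the possible loss is about one point of power, and the gain at r = 0.5 is about eleven (80.1 − 69.3).

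**Conclusion.** The concern holds as a question of efficiency. Row 1(i) leaves out a pre-randomisation score that the protocol's own FD data link to the outcome, and so probably gives up precision in the patient groups.

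At d = 0.8 and 20 per arm, the change in power from adjusting runs from −1.2 points (r = 0) through +2.9 (r = 0.3) and +6.2 (r = 0.4) to +10.8 (r = 0.5). Both r and d are assumptions, as is a common slope in the two arms. The case is best supported in FD. In DM it rests on Aim 1B being true. In controls there is no case for it. The documents do not support reading this as an invalid analysis or a biased estimate.

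**What to change.** In section 3.5, amend row 1(i) for FD and DM:

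- The main analysis within each group is a linear model of VAS on randomised arm plus the screening Nepean severity score. VAS is rank-transformed if the Gaussian check already planned there fails.
- Report the adjusted difference with its 95% CI.
- Keep the t-test or Wilcoxon test as a sensitivity analysis.
- For DM, state that the covariate is chosen on the assumption of Aim 1B.

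Keep the simple test in controls. Leave out age and gender. Do not use the two-week symptom diary as the covariate unless it is completed before the infusion; section 3.3(x) does not say when it is kept, and a diary filled in afterwards would not be a baseline measure.

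The change takes a sentence or two and needs no new data or visits. It costs one degree of freedom in each patient-group model, and about one point of power if the score does not predict VAS.

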Hence, we propose to evaluate the overall hypothesis that intestinal chemosensitivity related to increased epithelial permeability and GLP-1 explains symptom severity in patients with functional dyspepsia and in patients with DM and dyspepsia. 24 healthy subjects, 40 patients with DM and GI symptoms, and 40 patients with functional dyspepsia will undergo assessment of intestinal chemosensitivity during duodenal nutrient perfusion, gastric emptying (by scintigraphy), cardiovascular and GI vagal functions (plasma pancreatic polypeptide response to sham feeding and a comprehensive autonomic reflex screen), in vivo assessment of small intestinal permeability (urinary lactulose:mannitol ratio), and upper endoscopy with assessment of epithelial tight junction proteins and permeability on small bowel biopsies. During the nutrient infusion, subjects in each group (ie, healthy subjects, functional dyspepsia and DM) will be randomized to lipid infusion and placebo or lipid infusion {66.7 mL Microlipid (0.5 gm/mL diluted in water to 222 mL)} and exendin 9-39 in the ratio of 1:1. Hormonal responses (i.e., GLP-1, CCK, GIP, glucagon, PYY, C-peptide, and insulin) and plasma glucose will also be evaluated during enteral nutrient infusion. GI symptoms during each perturbation (meal, nutrient infusion) will be evaluated by validated questionnaires. Blood will be collected for DNA-based genetic analyses, initially to assess the relationship of GI sensorimotor dysfunctions and symptoms with SNPs affecting CCK and GLP-1 receptors. The analysis will assess for disturbances in these parameters in functional and DM dyspepsia, investigate associations between symptoms during enteral infusion and hormonal-epithelial functions, and evaluate relationships between daily symptoms and results of testing.

Table of Contents

ABSTRACT.....	1
1 SPECIFIC AIMS	3
2 BACKGROUND AND SIGNIFICANCE.....	5
3 RESEARCH DESIGN AND METHODS.....	7
3.1 Study Design.....	7
3.2 Study Subjects.....	7
3.3 Details of Study Assessments	8
3.4 Gene and Epigenetic Studies	15
3.5 Data Analysis	16
3.6 Potential Pitfalls.....	17
4 HUMAN SUBJECTS	17
5 SAFETY AND ADVERSE EVENTS	19
5.1 Definitions.....	19
5.2 Recording of Adverse Events	21
5.3 Reporting of Serious Adverse Events and Unanticipated Problems.....	22
5.3.1 Sponsor-Investigator reporting: notifying the Mayo IRB.....	22
5.3.2 Sponsor-Investigator reporting: Notifying the FDA.....	22
5.4 Stopping Rules	23
5.5. Medical Monitoring	23
APPENDIX.....	23

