3 RESEARCH DESIGN AND METHODS

3.1 Study Design

In addition to questionnaires, the primary study procedures include assessment of:

- i) Screening visit – The participant will undergo a physical examination if one has not been completed within the last 3 months.
- ii) Study day 1 - GI vagal function by sham feeding, autonomic functions, small intestinal permeability test and enteral nutrient infusion of lipids, to be performed in that order, on another day (Charlton 7 CRU)
- iii) Study day 2 – Women of child bearing potential will have a urine pregnancy test within 48 hours before the GI Transit study, Gastric emptying of solids and liquids and small intestinal transit on 1 day (Charlton 7 CRU)
- iv) Study day 3 - Upper gastrointestinal endoscopy with a small amount of fluid and intestinal biopsies

These tests will preferably be performed in the order listed above. (ii) must always be performed before (iv). Ancillary procedures include collection of blood for genetic and epigenetic studies and a stool sample for microbial assessment. Vital signs and nurse assessment will be performed at each visit.

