4 HUMAN SUBJECTS

Description: Studies will be conducted over 3 days. Subjects will be remunerated \$ 600. A screening assessment will be performed to ensure subjects fulfill entry criteria. Subjects will fast overnight prior to study days. Study procedures will be performed using established techniques by experienced technicians in our programs.

Research Materials: Blood samples (hormones, glucose, extract DNA and RNA) and stool samples will be obtained for this study.

Population and Recruitment of Subjects: Healthy subjects will be recruited from the community and patients with DM and dyspepsia will be recruited from the clinical practice and to patients who have provided research authorization. The Institutional Review Board will approve all recruitment materials. After discussing the study procedure and its risks, informed consent will be obtained, before study procedures. No children or prisoners will be recruited.

Potential Risks: Blood sampling. Blood samples are collected by venipuncture for this study. Assays for measuring blood glucose and plasma hormone will require 19ml blood at each of 18 time points during the enteral infusion study. The total blood drawn is 408 ml. Bruising can occur with venipuncture, as can fainting, etc. Risk Monitoring/Risk Reduction: The samples are collected using aseptic technique in the venipuncture area of the Clinical Research Unit where facilities are available should untoward reactions (fainting, etc.) occur. Given the aseptic nature of the sample collection and the small risk of bruising, the monitoring plan is focused on advising volunteers to call the co-investigators (physician) should they have unusual pain or discomfort from the venipuncture site.

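### Aim 1 item (ii) analyses an exendin-minus-placebo VAS delta that no subject can have; it should be specified as a group × treatment interaction

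*Combined protocol and SAP*

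**What the plan says.** The Aim 1 row of the analysis table in section 3.5 has two parts. Item (i) compares VAS between the exendin and placebo arms within each group, using a two-sample t-test or rank sum test. Item (ii) will "compare the delta VAS scores (exendin – placebo) to assess the association with subject status (FD,DM, and controls) using an ANOVA model". It names DM type as one possible covariate and offers Kruskal-Wallis as the alternative.

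The rest of the document describes a parallel design:

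- Abstract: "subjects in each group (ie, healthy subjects, functional dyspepsia and DM) will be randomized to lipid infusion and placebo or lipid infusion" with exendin 9-39.
- Section 3.3 item (v): lipid is given "together with placebo or exendin 9-39 in the ratio of 1:1".
- Section 3.1 schedules the infusion once, on study day 1: "small intestinal permeability test and enteral nutrient infusion of lipids". The other two study days are for transit and endoscopy.
- The sample size table in section 3.5 has arms of 12 versus 12 (controls), 20 versus 20 (FD) and 20 versus 20 (DM).
- Section 4, on blood sampling: assays "will require 19ml blood at each of 18 time points during the enteral infusion study. The total blood drawn is 408 ml".

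On power, section 3.5 says: "There is ~80% power (alpha =0.05, 2-sided) to detect the specified differences listed in the table below". The table lists exendin versus placebo within each group, and group versus group among subjects on exendin.

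**The concern.** A one-way ANOVA or Kruskal-Wallis test on deltas is the analysis of a crossover, in which each subject has a score under both infusions. Here each subject has one score, under one infusion. The listed test therefore does not match the data that will be collected.

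Item (ii) is the only listed analysis of whether the exendin effect differs between FD, DM and controls. Left as it is, the analyst would choose the model, the rank method and the coding of DM type after the data are in. A tempting substitute is to compare the item (i) p-values across groups. That does not test a difference in effect, and it would be distorted by having 12 per arm in controls and 20 per arm in patients.

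**Working it through.** **1. Does any subject have both scores?**

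- Arms: 12 + 12 = 24, 20 + 20 = 40 and 20 + 20 = 40. These equal the planned group sizes in section 3.2 (24, 40, 40; total 104), so every completer sits in exactly one arm.
- Blood: 19 mL × 18 = 342 mL for one infusion, within the 408 mL total. Two infusions would need 2 × 342 = 684 mL. (Section 3.3 gives the total as 403 mL; the conclusion is the same.)
- No second infusion, period, sequence or washout is described.

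Subjects contributing a delta: 0 of 104.

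**2. The plan's own power figure.** For the proportions in the sample size table, two-sided 0.05, with separate subjects in each arm:

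| Comparison | n | Rates | Pooled z | Fisher exact |
|---|---|---|---|---|
| Controls, exendin vs placebo | 12 vs 12 | 10% vs 68% | 88.2% | 79.3% |
| FD or DM, exendin vs placebo | 20 vs 20 | 10% vs 50% | 81.3% | 74.2% |
| Controls vs FD or DM, on exendin | 12 vs 20 | 10% vs 60% | 85.5% | 79.7% |
| FD vs DM, on exendin | 20 vs 20 | 30% vs 73% | 80.0% | 67.9% |

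The stated figure is broadly reproduced: pooled z gives at least 80% throughout, though no single method gives about 80% in all four rows. None of the rows compares exendin effects between groups.

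**3. What item (ii) can test.** The estimable quantity is a difference of differences: (exendin mean − placebo mean) in one group minus the same in another. With a common residual SD, its standard error in SD units is √(1/n₁ + 1/n₂ + 1/n₃ + 1/n₄).

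- Controls vs DM, or controls vs FD: √(2/12 + 2/20) = 0.516.
- DM vs FD: √(2/20 + 2/20) = 0.447.

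Residual degrees of freedom: 104 − 6 cells = 98. From the noncentral t, 80% power at two-sided 0.05 needs 2.83 standard errors.

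- Controls vs DM or FD: 2.83 × 0.516 = 1.46 SD.
- DM vs FD: 2.83 × 0.447 = 1.27 SD.
- Power at a true difference of 0.8 SD: 33.5% and 42.5%.
- Overall 2-df interaction test: needs 1.47 SD if only controls differ and 1.27 SD if only DM differs; power at 0.8 SD is about 31% and 40%.
- For comparison, item (i) detects 1.20 SD (12 vs 12) and 0.91 SD (20 vs 20).

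The documents give no SD for the VAS. If it were 20 to 30 mm (an assumption), 1.46 SD is about 29 to 44 mm and 1.27 SD about 25 to 38 mm on the 100 mm scale.

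**4. Illustration from the table's rates.** The listed differences are 68 − 10 = 58 points in controls and 50 − 10 = 40 points in patients, an interaction of 18 points. Its standard error is √(0.10×0.90/12 + 0.68×0.32/12 + 0.10×0.90/20 + 0.50×0.50/20) = 0.206, giving about 14% power. The table's rates are detectable differences, not expected ones, so this shows scale only.

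**5. Type of DM.** Added to group × treatment as a none/1/2 factor, it gives 8 design columns of rank 7, because its no-diabetes level carries the same information as group. Nested within DM it gives 7 columns of rank 7 and is estimable.

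**6. Rank alternative.** Simulation with the planned cell sizes, Gaussian errors, no true interaction and 6,000 runs: with a treatment effect of −2 SD and a patient-group effect of +2 SD, type I error of the interaction F test was 4.5% on raw VAS, 11.3% on simple ranks and 4.7% on aligned ranks. With 1 SD effects all three were about 5%.

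**The case against.** The strongest reply is that the ANOVA half is only loosely worded. Item (i), in the same table cell, uses independent-sample tests, so delta can be read as the arm difference within each group, and comparing that by ANOVA is the interaction. That reading is reasonable, but it arrives at the same correction: the plan names no interaction term, and Kruskal-Wallis fails on either reading. Some phrases hint at paired data (with and without exendin in Aim 2, plural infusions in section 3.5, sampling during each study under the blood table), but none schedules a second infusion.

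A second reply concerns weight. No stated hypothesis asks whether the exendin effect differs by group. Aim 2B, that exendin reduces chemosensitivity, is answered by item (i). This stands, and it is why the interaction should be labelled exploratory. The power statement also confines itself to the tabulated differences, so it makes no false claim about item (ii).

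Three further points stand as refinements. The interaction does not answer Aim 1A (DM versus controls), which needs its own named contrast. Splitting DM into two types raises the detectable sizes. The simulation used Gaussian errors and large effects, whereas the fallback is meant for non-Gaussian VAS; aligned ranks also held about 4–6% type I error in runs with skewed data, so the recommendation survives although the quoted run is weak evidence for it.

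**Conclusion.** The concern holds. Item (ii) cannot be run on individual deltas, and on the charitable reading it is an interaction test that the plan does not specify, with a rank alternative that cannot perform it. The trial can detect only large differences in exendin effect between groups: 1.46 SD for controls versus either patient group and 1.27 SD for DM versus FD. These are unadjusted pairwise contrasts and assume 104 completers, the planned arm sizes and a common SD across the six cells. The millimetre equivalents rest on an assumed SD. Item (i) is unaffected. The fault lies in the analysis specification and should be corrected before the data are analysed.

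**What to change.** Keep item (i). Replace item (ii) as follows.

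- **Model:** a two-way between-subject linear model for VAS with group, treatment and group × treatment; the interaction tests whether the exendin effect differs by group. Age and sex may be added, since the groups are only frequency-matched on them; with 96 residual df the detectable sizes are essentially unchanged (1.461 and 1.266 SD).
- **Non-Gaussian VAS:** an aligned-rank test of the interaction in place of Kruskal-Wallis. A simple rank transform is less safe when main effects are large.
- **Type of DM:** a term nested within DM, or four group levels (control, FD, type 1, type 2). If four levels are used with an even split (10 per arm for each type), state the larger detectable sizes: 2.83 × √(2/12 + 2/10) = 1.71 SD for control versus one type, 2.83 × √(2/20 + 2/10) = 1.55 SD for FD versus one type, and 2.83 × √(4/10) = 1.79 SD for type 1 versus type 2.
- **Status:** label the interaction exploratory, give its detectable size, and say that the stated power of about 80% does not cover it.
- **Aim 1A:** name a separate DM-versus-control contrast, for example in the placebo arms.
- **Optional:** report the group-adjusted exendin main effect as an overall test of Aim 2B. With 52 versus 52 the standard error is √(2/52) = 0.196 SD, and about 0.55 SD is detectable if the effect is similar across groups.

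The cost is plan wording and a little programming, with no new subjects or data. The one drawback is that the plan must acknowledge low power for comparing exendin effects between groups.
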